### **3.7 Self-Monitoring Fasting Blood Glucose and Patient Diaries**

All patients will self-monitor fasting morning blood glucose levels three (3) times weekly during the run-in and treatment period. Monitoring must be performed at the same time each designated day ( $\pm$  10 minutes) prior any caloric intake. Patients will be required to record the values in a patient diary and bring the diary to each clinic visit. Information recorded for the fasting blood glucose will be reviewed by the clinical research coordinator for completeness and transcribed onto electronic case report form (eCRF). During the study, both fasting finger stick glucose and laboratory fasting plasma glucose will be obtained.

If a fasting blood glucose measures greater than or equal to 270 mg/dL (15 mmol/L) during daily self-monitoring or during any in-clinic visit, the patient will be required to contact the clinic to report the value. The patient may be required to return for an unscheduled visit to the clinic for a repeat measurement of fasting blood glucose within one week after the original measurement. If

the patient is invited for an unscheduled visit, blood will be drawn and sent to lab for plasma glucose determination. If the repeat measurement is also greater than or equal to 270 mg/dL, the patient will be discontinued from treatment with study drug and offered rescue medication. The patient will continue to be seen for all remaining study visits, if possible.

If a fasting blood glucose value is <70 mg/dL, the patient should drink 1 cup of orange juice or swallow 3-4 glucose tablets. The patient must check his blood sugar after 10 min and if the blood glucose level does not raise, the patient needs to drink another cup of orange juice or swallow 3-4 glucose tablets. Blood sugar must be checked again after 10 minutes. The patient must call to report this event to the study site and record all blood glucose levels in the diary.

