If three or more fingerstick glucose values of <50 mg/dL (2.78 mmol/L) are observed within 12 hours subsequent to administration of study drug without a reasonable explanation (such as increased physical activity and/or skipped meal), the patient will be discontinued from treatment with study drug and rescued with glucose administration (20g of glucose tablets) which will be available at all times at the study site. This information will be recorded in the patient's diary and the patient will be instructed to contact the study site if this occurs. The patient will continue to be seen for all remaining study visits.

Sites will instruct patients to immediately perform a finger stick glucose measurement if any symptoms occur that may be related to hypoglycemia (e.g., weakness, dizziness, shakiness, increased sweating, palpitations, or confusion), and to avoid delay in treating these symptoms. The measurements will be recorded in the patient diary. Patients will always carry glucose tablets with them and ingest 3-4 tablets if hypoglycemia occurs.

Hypoglycemia and associated symptoms (e.g., weakness, dizziness, shakiness, increased sweating, palpitations, or confusion), have been associated with insulin administration, including ORMD-0801.

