### 4.3 Subject and Trial Discontinuation

Subjects may choose to withdraw from this study at any time for any reason without penalty of jeopardizing their health care or loss of benefits to which the subject is otherwise entitled.

Within the provisions of informed consent and good clinical judgment with respect to safety, every attempt will be made to have subjects complete the study. The following are reasons to terminate a subject's participation in the study:

1. Subject experiences an AE that in the judgement of the Investigator poses a significant risk to the subject for continued participation in the study.
2. Subject uses any medication that in the judgment of the Investigator poses a significant risk to the subject for continued participation in the study or that will interfere with the interpretation of the results of the study.
3. Subject becomes pregnant.
4. Significant protocol violation or noncompliance on the part of the subject or the Investigator.
5. Intercurrent illness that requires treatment that is not consistent with the protocol requirements, or intercurrent illness or the associated treatment that in the judgment of the Investigator poses a significant risk to the subject for continued participation in the study.
6. Subject wishes to withdraw for any reason.
7. Sponsor elects to end the study, or the Investigational Site elects to end the study at their site.
8. Any other reason that in the judgment of the Investigator poses unacceptable risk to the subject.

Subjects who withdraw from the study prior to treatment may be replaced. Subjects who are withdrawn and have received at least one treatment will not be replaced. Subjects who discontinue study drug treatment will not be replaced.

Except in cases of emergency, the Investigator should consult with the Sponsor and the Medical Monitor before removing the subject from the study. In some circumstances it may be necessary to temporarily interrupt treatment as a result of AEs that may have an unclear relationship to the IMP. The Investigator should obtain approval from the Sponsor and Medical Monitor before restarting IMPs that were temporarily discontinued for an AE.

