### 7.5.1 Routine Reporting of Adverse Events

All AEs, whether or not associated with the IMP that are observed by the Investigator, other Investigational Site personnel, or those reported by the subject will be recorded in the subject's source documentation and on the AE page of the eCRF. Copies of the SAE eCRF pages or an SAE listing generated based on the eCRF pages will be submitted to the Sponsor at regularly scheduled intervals to allow the Sponsor to meet expedited regulatory reporting requirements under 21 CFR 312.32 and regular regulatory reporting requirements under 21 CFR 312.33.

For each AE, the following information will be entered in the eCRF:

- Medical diagnosis of the event in standard medical terminology (if a medical diagnosis cannot be determined, a description of each sign or symptom characterizing the event);
- Date of onset of any new AE or worsening of a previously observed AE. For the days when the subject is in the clinic (Visit 2 to Visit 9), the time (based on a 24-hour clock) of onset should be recorded if available;
- Date of resolution of the event (or confirmation ongoing). For the days when the subject is in the clinic (Visit 2 to Visit 9), the time (based on a 24-hour clock) of resolution should be recorded if available;
- Whether the event is serious (per definition in [Section 7.4](#)), and if so, the reason it is considered serious;
- Severity of AE (per definition in [Section 7.7](#));
- Assessment of the attributability of the AE to the IMP [per definition in [Section 7.5](#)];
- Expectedness of AE (per definition in [Section 7.8](#));
- Action taken in treating the AE (including concomitant medications or therapies administered) and/or change in the IMP administration or dose (including whether the IMP was temporarily interrupted or discontinued);
- Outcome of AE (per definition in [Section 7.9](#)).

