### 8.2 Safety Evaluation

#### 8.2.1 Adverse Events

AEs will be coded using the most current version of MedDRA. The severity of AEs will be graded according to NCI CTCAE version 4.03. AEs will be regarded as “pretreatment” if they occur during the Placebo Run-in Phase. TEAEs are defined as any AE that starts or increases in severity after the first dose of IMP at Visit 3.

The incidence of TEAEs will be tabulated by MedDRA preferred term, system organ class, treatment group, severity, and assigned relationship to IMP. The incidence for each TEAE will be provided as the total number of subjects that experienced the TEAE, as well as the percentage of the population that this represents. If a TEAE is reported more than once for a given subject, the greatest severity and the worst-case attribution will be presented in the summary tables.

TEAEs will be listed for individual subjects, along with information regarding onset and end dates, onset time where available, severity, seriousness, relationship to IMP, action taken, and outcome. A similar listing will be prepared for the pretreatment AEs.

Pretreatment AEs and TEAEs that lead to withdrawal from the study will be separately listed and summarized. Similarly, separate tabulations and listings will be prepared for pretreatment and treatment emergent SAEs.

Descriptive statistics will be generated as appropriate (i.e., frequency for categorical data). Inferential statistical analysis comparing the AE data between Active treatment and Placebo is not planned.

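### The separate summary of AE discontinuations covers only withdrawal from the study, so subjects who stop study drug but stay in follow-up are not counted, and no by-arm count of drug stops is planned

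*Combined protocol and SAP*

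**What the plan says.** Safety is the primary endpoint (Section 2.3), and Section 8.2.1 plans no inferential comparison of AEs, so the descriptive tables carry the primary result. For events that end participation, Section 8.2.1 says: "Pretreatment AEs and TEAEs that lead to withdrawal from the study will be separately listed and summarized".

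Section 3.7 sets two glucose rules that stop study drug:

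- **High glucose.** If a repeat fasting value is again at or above 270 mg/dL, "the patient will be discontinued from treatment with study drug and offered rescue medication". On follow-up: "The patient will continue to be seen for all remaining study visits, if possible".
- **Low glucose.** After three or more unexplained fingerstick values below 50 mg/dL within 12 hours of dosing, "the patient will be discontinued from treatment with study drug and rescued with glucose administration". On follow-up, without qualification: "The patient will continue to be seen for all remaining study visits".

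Section 4.3 first sets replacement rules for subjects who withdraw, then adds a separate rule for drug stops: "Subjects who discontinue study drug treatment will not be replaced".

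Section 7.5.1 has the eCRF record, for each AE, any "change in the IMP administration or dose (including whether the IMP was temporarily interrupted or discontinued". Section 8.2.1 uses that field only in the individual TEAE listing, which shows "severity, seriousness, relationship to IMP, action taken, and outcome".

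**The concern.** The criterion in Section 8.2.1 is leaving the study. The stops that the protocol defines in advance for this insulin product do not make the subject leave; they end dosing while visits go on. A subject managed exactly as Section 3.7 instructs therefore falls outside the summary.

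How many subjects in each arm had to stop drug because of an event is a main tolerability result. Hypoglycemia is the only AE of special interest in Section 7.3. If the report shows no AEs leading to study withdrawal, a reader could take this to mean that nobody had to stop drug, and no planned table would correct that impression.

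**Working it through.** The plan states no figure on this point, so there is nothing to reproduce. The check is a comparison of sections, followed by a statement of scale.

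**1. Where a drug stop goes under the planned outputs**

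| Output | Low-glucose stop, visits continue | High-glucose stop, visits continue |
|---|---|---|
| Summary of AEs leading to study withdrawal (8.2.1) | Not counted | Not counted |
| TEAE incidence table (8.2.1), by preferred term, organ class, arm, severity and relationship | The hypoglycemia event is counted, because Section 7.5 makes it an AE; the fact that drug was stopped is not shown | Counted only if the site records the high glucose as an AE |
| TEAE listing (8.2.1) | Drug stop shown under action taken | Shown only if recorded as an AE |
| Disposition, exposure and study termination (Synopsis, Statistical Methods) | Shorter exposure; no stated count of drug stops by reason | Same |

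No row gives a by-arm count of events that stopped drug.

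**2. Whether high glucose is an AE.** Section 7.5 says expressly that hypoglycemic events are AEs. There is no matching statement for hyperglycemia. The general definition in Section 7.2 includes abnormal laboratory findings, so a site may record it, but this is left to judgment. A high-glucose stop can therefore miss every AE output.

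**3. Scale.** Inputs: approximately 36 randomized 2:1 (Section 5.2). Assumptions: exactly 36, an exact split, and all treated.

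- Active: 36 × 2/3 = 24. One subject = 1/24 = 4.2 percentage points.
- Placebo: 36 × 1/3 = 12. One subject = 1/12 = 8.3 percentage points.

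**4. How likely it is to arise.** The documents give no rate of drug stops. For an assumed rate p among 24 active subjects, the expected number is 24p and the chance of at least one is 1 − (1 − p)^24:

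| Assumed p | Expected number | Chance of at least one |
|---|---|---|
| 2% | 0.5 | 38% |
| 5% | 1.2 | 71% |
| 10% | 2.4 | 92% |
| 15% | 3.6 | 98% |

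If these subjects all stay in the study, the planned withdrawal summary shows none of them, whatever p is.

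**The case against.** **The events are still reported.** A hypoglycemia event after the first dose at Visit 3 enters the TEAE incidence table by arm, and the listing shows that drug was stopped. This stands. A reader might infer that such stops disappear from the primary safety reporting; the documents do not support that. Only the tabulation of drug stops is missing.

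**The direction of any distortion is not shown.** It is tempting to conclude that the rule makes the active arm look better tolerated, since hypoglycemia is the expected effect of insulin. But the same criterion also omits high-glucose stops, which could fall more on placebo if the drug lowers glucose, and it omits drug stops for unrelated AEs in either arm. With no stop rates in the documents, the net direction is unknown.

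**Some of these subjects may be counted after all.** After a high-glucose stop, continued visits are required only where feasible. Under Section 4.3, an AE that the investigator judges a significant risk ends study participation. Terms are also used loosely: Section 5.4 refers to Section 4.3 for when dosing ends, although that section lists reasons for ending participation. This shows that the omission is not absolute and may not be deliberate. It does not change what the criterion says, and Section 4.3 does separate the two states.

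**More detail may follow.** Section 8 defers additional details to a statistical analysis plan, and no fuller text on this point is in the document reviewed. Such a plan could add the table. The point is therefore limited to what Section 8 specifies, and the criterion stated there would still need changing.

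**The study is small and exploratory.** Section 8.1 says that it is not powered for significance. No test, population or data collection is wrong here. This lowers the severity but does not remove the point, because the descriptive safety tables are the primary result.

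**Conclusion.** The point holds in limited form. Section 8.2.1 separately summarizes AEs leading to study withdrawal only, so subjects who stop study drug under Section 3.7 and remain in follow-up are not counted there. No by-arm count of events that stopped drug is planned elsewhere in the document. The gap may be wider for high glucose, where the stop need not be recorded as an AE.

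The per-subject sizes in the working depend on the assumed 24 and 12 treated subjects. The number of subjects affected cannot be derived from the documents, and neither the complete loss of these events nor a bias in favor of the active arm is established. Severity: should-fix.

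**What to change.** In Section 8.2.1:

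1. Summarize by arm the TEAEs leading to permanent discontinuation of study drug, using the action-taken field of Section 7.5.1. Keep this separate from the summary of TEAEs leading to withdrawal from the study.
2. Tabulate by arm the number of subjects stopped under each Section 3.7 glucose rule, whether or not the stop was recorded as an AE. This captures the high-glucose stops that the first table could miss.

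The inputs are already collected: the action-taken field, the glucose values transcribed to the eCRF (Section 3.7) and the record of IMP administration (Section 5.6). The cost is a change of wording and one or two extra tables, with no new data and no change to the clinical stopping rules. The wording should be settled before unblinding.

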### 8.2.2 Laboratory Evaluations

Individual clinical safety lab (hematology, serum chemistry and serology) values will be listed by visit and summarized using descriptive statistics as appropriate (i.e., mean, median, range, and standard deviation for continuous data and frequency for categorical data). Individual change from baseline (Screening) in laboratory values will be calculated and summarized descriptively. Shift tables from baseline (Screening) to post-dose (Visit 8) will also be produced for the laboratory assessments based on the categories of Low, Normal, and High. A clinically significant change from baseline will be recorded as an AE if deemed appropriate by the Investigator.

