Subjects will then undergo a Treatment Phase consisting of a treatment period of 12 weeks that will start at Visit 3 (Week 0) and outpatient visits at Weeks 1, 2, 4, 8, and 12 (final visit). At each visit, concomitant medication will be reviewed, weight will be measured, and sufficient quantity of medication will be dispensed to last until the next nominal clinic visit. Medication compliance check will be performed, self-monitored fasting morning blood glucose (finger-stick) will be recorded 3 days weekly in the morning and subjects' diaries will be reviewed. Vital signs (SBP/DBP, heart rate and oral temperature) will be recorded. Adverse events will be monitored and recorded. ORMD-0801 morning treatment will be administered in clinic during Visits 3, 6 and 7.

At Visit 3, urine pregnancy test will be performed for females of childbearing potential. At Visit 8, subjects will have HbA1c evaluations and MRI-PDFF performed. At Visits 3 and 8, a complete physical exam and CAP-Fibroscan will be performed.

At Visits 3 (baseline), 6, 7, and 8, patients will have clinical laboratory evaluations (serum chemistry, hematology) and blood lipids performed. Fasting blood glucose, insulin (also used for HOMA estimates) and adiponectin levels will be measured.

The End-of-Study (EOS) Visit (Visit 9) will be conducted 4 weeks following the last scheduled treatment visit. Subjects concomitant medications will be reviewed, and weight will be measured. A complete physical exam and ECG will be performed and vital signs (SBP/DBP, heart rate and oral temperature) will be measured if deemed necessary by the investigator. Clinical laboratory evaluations [serum chemistry (including liver function tests (LFTs) and blood lipids) and hematology] will be performed. Fasting blood glucose, fasting insulin, HbA1c and adiponectin levels will be measured. Subject diaries will be collected and reviewed for self-monitored fasting morning blood glucose. Adverse events will be monitored and recorded. Subjects who are discontinued early from the study will complete the EOS evaluations at the time of early discontinuation.

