## Table 1 Footnotes

-  Prior and concomitant medications will be reviewed at Screening. Concomitant medications will be reviewed through Visits 2-9.
-  Only if investigator deems necessary.
-  Height measurement and BMI calculation will be performed at Screening only. Weight will be measured as indicated.
-  Serum pregnancy test will be performed at Screening (Visit 1). Urine pregnancy test will be performed at Visit 2 and Visit 3.
-  Blood samples taken prior to dosing in clinic and snack provided after 30-45 minutes at Visit 2, 3, 6, and 7.
-  Study medication will be dispensed and collected at Visits 2-8 and collected at End-of-Study/Early Termination Visit.
-  Vital signs (blood pressure, heart rate, oral temperature). Vital signs will be measured in the sitting position after at least 5 minutes of rest.
-  Serum Chemistry: Sodium, Potassium, Glucose, BUN, Creatinine, BUN/Creatinine, Chloride, Calcium, Protein, Albumin, Globulin (total), A/G Ratio, SGOT (AST), SGPT (ALT), Bilirubin (total), Alkaline Phosphatase, CO2, Creatine Phosphokinase (CPK), Total cholesterol, LDL, HDL, Triglycerides, Thyroid Stimulating Hormone (TSH, screening only). Hematology: Hemoglobin, Hematocrit, RBC, WBC (total count and differential count), Platelets Count, Mean Platelet Volume (MPV), MCV, MCH, MCHC, RDW, Neutrophils (absolute value and %), Bands (ABS CNT), Bands, Lymphocytes (absolute value and %), Monocytes (absolute value and %), Eosinophils (absolute value and %), Basophils (absolute value and %), RBC Morphology. Urinalysis is not performed in this study.
-  Fasting blood glucose and insulin will be used to determine Homeostasis Model Assessment (HOMA) estimates. During an Unscheduled Visit only fasting blood glucose will be collected, if investigator deems necessary.
-  Self-monitoring (finger-stick) of fasting blood glucose will be required 3 days weekly in the morning, before breakfast, and recorded in patient diaries.
-  HCV-Ab (hepatitis C virus antibody), HBsAg (surface antigen of the hepatitis B virus), HBcore-total (total hepatitis B core antibody), HBs Ab (hepatitis B surface antibody), anti-HIV Ab (human immunodeficiency virus antibody).

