### 8.2.3 Vital Signs

Individual vital sign measurements (seated SBP/DBP, heart rate and oral temperature) will be listed by measurement time and summarized using descriptive statistics as appropriate (i.e., mean, median, range, and standard deviation). Individual change from baseline (screening) in vital sign measurements will be calculated and summarized descriptively. A clinically significant change from baseline will be recorded as a TEAE if deemed appropriate by the Investigator.

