### 8.2.5 Physical Examination

Individual physical examination findings will be listed by visit. A clinically significant change from baseline (Screening) will be recorded as an AE if deemed appropriate by the Investigator.

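### Laboratory and vital-sign change is measured from Screening rather than from the last pre-dose value at Visit 3, so a laboratory crossing that arose before dosing and persists to Visit 8 is tabulated as a post-dose shift

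*Combined protocol and SAP*

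**What the plan says.** Section 8.2.2 sets the reference for laboratory change: "Individual change from baseline (Screening) in laboratory values will be calculated and summarized descriptively". It uses the same reference for the one Low/Normal/High table that the plan names: "Shift tables from baseline (Screening) to post-dose (Visit 8) will also be produced for the laboratory assessments". Section 8.2.3 follows suit for vital signs, "Individual change from baseline (screening) in vital sign measurements will be calculated and summarized descriptively", and then adds "A clinically significant change from baseline will be recorded as a TEAE if deemed appropriate by the Investigator". Section 8.2.5 also refers physical examination findings to Screening: "A clinically significant change from baseline (Screening) will be recorded as an AE if deemed appropriate by the Investigator".

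Two other places start the clock at Visit 3. Section 3.1 says "At Visits 3 (baseline), 6, 7, and 8, patients will have clinical laboratory evaluations", which attaches the baseline label to Visit 3 for chemistry, hematology and lipids. Section 8.2.1 says "TEAEs are defined as any AE that starts or increases in severity after the first dose of IMP at Visit 3".

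Visit 3 supplies a usable pre-dose value. Table 1 schedules laboratory tests and vital signs at both Screening and Visit 3, and its footnote 5 reads "Blood samples taken prior to dosing in clinic and snack provided after 30-45 minutes at Visit 2, 3, 6, and 7". Section 6.5.2 puts vital signs ahead of any blood draw at the same time point, so the Visit 3 vital signs are also pre-dose, by inference.

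**The concern.** Safety is the primary endpoint, and its parts start from different points: adverse events from the first randomized dose, laboratory and vital-sign change from a visit up to six weeks earlier. The interval between the two contains the two-week placebo run-in. Anything that moves a laboratory value in that interval enters the on-treatment change, and a persisting category change enters the shift table under a post-dose column.

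The arms hold about 24 and 12 subjects, and safety is summarized descriptively. A reader will look at small counts within each arm, so whether one or two subjects crossed a limit before or after dosing matters for interpretation. A programmer also has two different visits labelled baseline for the same laboratory tests.

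**Working it through.** **Documents.** The plan gives no figure of its own to reproduce, so the check traces the reference visit and then works out the time and classification that follow.

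1. Timing, in nominal days. Screening is at most 42 days before the Treatment Phase (Sections 3.1 and 3.2). It precedes Visit 2 at Day -14, so 14 days is the lower limit. Visit 3 to Visit 8 is 84 days.
   - Shortest case: 14/(14 + 84) = 14/98 = 14% of the Screening-to-Visit-8 interval is pre-dose.
   - Longest case: 42/(42 + 84) = 42/126 = 33%.
   - With Visit 3 as reference the interval is 84 days, none of it pre-dose.

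2. Classification, read directly from the definitions:

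| Screening | Visit 3 (pre-dose) | Visit 8 | Table as written | Table from Visit 3 |
|---|---|---|---|---|
| Normal | High | High | Post-dose shift | No shift |
| High | Normal | High | No shift | Post-dose shift |
| Normal | High | Normal | No shift | High to Normal |
| Normal | Normal | High | Post-dose shift | Post-dose shift |

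3. Net count. Write N and H for the categories at Screening, Visit 3 and Visit 8 in order.
   - P(Normal-to-High from Screening) = P(NNH) + P(NHH)
   - P(Normal-to-High from Visit 3) = P(NNH) + P(HNH)
   - Difference = P(NHH) − P(HNH)

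   The misattributed and the hidden subjects therefore offset each other in the total.

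**Illustration on assumed values.** The documents give no prevalence or between-visit correlation. Assume no drug effect, a normally distributed marker, 10% to 25% of values above the upper limit (Normal meaning not above it), and either equal correlation between visits (0.5 to 0.85) or correlation decaying with time (28-day r of 0.70 to 0.95).

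One case in full: 10% above the limit, 28-day r = 0.85, Screening at Day -42.
- Correlations: Screening–Visit 3, 0.85^(42/28) = 0.78; Visit 3–Visit 8, 0.85^(84/28) = 0.61; Screening–Visit 8, 0.85^(126/28) = 0.48.
- Normal-to-High probability is 0.069 from Screening and 0.060 from Visit 3.
- Of 24 active subjects, 0.39 are misattributed (24% of tabulated shifts) and 0.18 are hidden (12% of Visit-3-to-Visit-8 crossings).
- Net excess: 0.39 − 0.18 = 0.21 of 24.

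Across the assumed range, per analyte:

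| Setting | Misattributed, of 24 | Hidden, of 24 | Net excess, of 24 | SD of change, Screening / Visit 3 |
|---|---|---|---|---|
| Equal correlation | 0.34–1.12 | 0.34–1.12 | 0 | 1.00 |
| Decaying, Day -14 | 0.17–0.63 | 0.10–0.47 | 0.06–0.17 | 1.04–1.07 |
| Decaying, Day -42 | 0.32–1.08 | 0.14–0.68 | 0.16–0.45 | 1.10–1.20 |

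The misattributed share of tabulated Normal-to-High shifts is 11% to 43%, and the hidden share of true crossings is 8% to 43%. Among subjects Normal at Screening and High at Visit 3, 43% to 78% are Normal again at Visit 8 and never enter the table as a shift. The counts are not bounds: at 2% to 5% above the limit the misattributed number is 0.02 to 0.20 of 24, and at 50% it is 0.5 to 2.1.

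**The case against.** The best case for the plan has four parts.

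- Section 8 is deliberate and consistent: 8.2.2, 8.2.3 and 8.2.5 all name Screening, and the contrary label in 3.1 is one parenthesis in a design overview. This stands as far as it goes. It makes the conflict one between sections and does not settle which reference answers the safety question.
- Screening is the only safety-laboratory value before any study capsule, because Visit 2 has no clinical laboratory panel. The run-in capsules are placebo, described as fish oil, and the active formulation also contains fish oil. A Visit 3 baseline would absorb any run-in effect. That is a real, small cost. But the documents do not give it as a reason, and a pre-run-in reference does not isolate change after randomized drug.
- The table reports categories at two visits and makes no claim about onset. Strictly true, but its second column is called post-dose, and it is the only laboratory shift table named.
- Values are listed and summarized by visit, and the synopsis promises changes at each time point, so Screening-to-Visit-3 drift will be visible. This limits the harm but leaves the shift table itself uncorrected.

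A reader might go further and infer bias in favour of or against the active arm. The documents do not support that: both arms pass through the same screening and placebo run-in. Nor does the sentence in 8.2.3 inflate the treatment-emergent count by itself. It depends on investigator judgement, and the onset rule in 8.2.1 still governs. It is loose wording that conflicts with that rule without overriding it.

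**Conclusion.** The point holds and is minor. Two things follow from the documents alone: the baseline label conflicts between Section 3.1 and Section 8, and the shift table counts persisting pre-dose crossings as post-dose while hiding some on-treatment ones. The pre-dose share of the interval, 14% to 33%, is a share of nominal days; it should not be read as a share of shifts.

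The effect is on attribution, and possibly noise, within each arm. Under the stated assumptions the net excess of Normal-to-High shifts is 0 to 0.45 of 24 active subjects per analyte, and the SD of change is 0% to 20% larger. These figures illustrate scale only, since prevalence and correlation are assumed and the model ignores selection of subjects on Screening values. The study is exploratory and not powered for significance, and no inferential comparison of adverse events is planned, so no formal conclusion depends on this choice.

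**What to change.** Make four wording changes before the tables are programmed, and carry them into the statistical analysis plan to which Section 8 leaves further detail.

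- In 8.2.2, 8.2.3 and 8.2.5, define the analysis baseline as the last non-missing assessment before the first randomized dose: normally Visit 3, otherwise Screening. Including 8.2.5 matters because a physical examination is also done at Visit 3; leaving it on Screening would create a new split within Section 8.2.
- Keep Screening only for measures without a Visit 3 assessment, for example HbA1c, ECG and MRI-PDFF.
- Align the label in 3.1 with that definition.
- Reword 8.2.3 so that a clinically significant change is recorded as an adverse event if the investigator judges it appropriate, with its class (pretreatment or treatment-emergent) decided by the onset rule in 8.2.1.

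No new data are needed, since the Visit 3 assessments are already scheduled. The one cost is that any effect of the run-in capsules moves into the baseline; the Screening values in the by-visit listings and summaries keep it visible.
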